8.2.4.3 Biomarker: Assess PD-1/PD-L1 DNA methylation status by bisulfite-sequencing assay

To assess PD-1/PD-L1 DNA methylation status geometric means of PD-1/PD-L1 methylation levels (expressed as percentage) will be reported at baseline and at the start of cycle 3. The change in geometric mean methylation levels from baseline to start of cycle 6 will be reported as the ratio of geometric means and tested for difference from one using a paired t-test on log transformed data.

8.2.4.4 Biomarker: Assess status and change in PD-1/PD-L1 expression with response to therapy.

To assess status and change in PD-1/PD-L1 expression with response to therapy, the proportion of patients responsive to treatment following their 6th cycle will be computed and compared between PD-1/PD-L1 positive and negative patient groups, with positivity based on 3rd cycle expression levels, using a Fisher's exact test of association.

8.2.4.5 Biomarker: Assess changes in driver mutation burden (*JAK2V617F*, *MPLW515L/K*, *CALR*) in granulocytes from treated patients at diagnosis, after 6 cycles and at 1 year of pembrolizumab therapy and correlate with response to therapy.

To assess the correlation between changes in driver mutation burden from diagnosis to 1 year of pembrolizumab therapy and response to therapy, the median *JAK2V617F*, *MPLW515L/K* and *CALR* allele burden (expressed as a percentage) will be computed at baseline, after 6 cycles of treatment and at 1 year, with significant changes from baseline evaluated using the Wilcoxon signed rank test at each of the two follow-ups. Among patients positive for each mutation, a linear mixed-effects model will be fit to log-transformed allele burden data with

Product: MK-3475

Protocol/Amendment No.:

patient as the random effect and time points as the fixed effect. The mean changes from baseline in PD-1 and PD-L1 and their standard errors will be derived at each time point from the model.

8.2.4.6 Biomarker: Evaluate changes in Immune response gene expression profile as well as tumor microenvironment in bone marrow biopsy specimens using nanostring technology after 6 cycles of treatment with pembrolizumab.

To evaluate changes in immune response, we will identify and characterize the gene expression signatures of both the global immune status as well as for each of the functional biological processes before therapy as well as at 6 cycles and 1 year post therapy. The regulation of these complex immunological processes involves hundreds of genes, many of which function in multiple biological processes. We anticipate that cases with different molecular make-up or outcome may have different immune response / microenvironment gene expression signature either in the global immune response level or at the level of selective functional biological process such as T-cell functions, cytokines or possible extracellular matrix constituents, thereby could propose relevant immune response and potential resistance mechanisms to therapy.

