2.1 Trial Design

This is a multicenter, open-label, Phase 2 study to assess the efficacy, safety and tolerability of pembrolizumab in patients with chronic phase myelofibrosis (MF-CP) defined as either patients with primary myelofibrosis (PMF), post essential thrombocythemia (post-ET) or polycythemia vera (post-PV) myelofibrosis (primary cohort). We propose a Simon-two stage design for this study. We will test pembrolizumab at the FDA approved dose (in head and neck cancer) of 200mg dose administered via intravenous infusion over 30 minutes given every 3 weeks. Nine patients will be enrolled in the first stage of the Simon-two stage design, and 15 in the second stage. A treatment cycle is 3 weeks and the core study period is 6 cycles. Response assessment by established consensus criteria will be used to assess response after 6 cycles in order to determine if the trial will progress to the second stage and for the purpose of determining the primary endpoint. In addition, we will allow a maximum of ten patients with accelerated or blast phase disease (MPN-AP/BP) who are refractory or intolerant to conventional therapies such as decitabine, and in which hematopoietic stem cell transplant is not a therapeutic option (exploratory cohort), to enroll in the study as a separate exploratory cohort. These patients can be enrolled during stage 1 or 2 and they will be analyzed separately from the primary cohort population. The study will therefore enroll a maximum of 34 patients.

The study will enroll at 3 centers (Mount Sinai, NY; Montefiore, NY; Massachusetts General Hospital, MA).

Exploratory biomarkers will be obtained from enrolled patients at baseline, cycle 3 and cycle 7 and at 1 year of therapy. Patients that obtain at least a clinical improvement after 6 cycles of therapy can continue receiving pembrolizumab until evidence of disease progression, unacceptable toxicity, and patient or physician decision for a maximum of 2 years.

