
Pembrolizumab is a potent and highly selective humanized monoclonal antibody (mAb) of the IgG4/kappa isotype designed to directly block the interaction between PD-1 and its ligands, PD-L1 and PD-L2. KeytrudaTM (pembrolizumab) has recently been approved in the United States for the treatment of patients with unresectable or metastatic melanoma and disease progression following ipilimumab and, if BRAF V600 mutation positive, a BRAF inhibitor.

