The loss of anti-tumor immunity mediated by PD-1/PD-L1 signaling through aberrant expression of PD-L1 by the malignant cells has been well documented in solid tumors and serves as a novel and potent therapeutic target in many malignant disease types such as melanoma, lung cancer, lymphoma and others. The role of PD-1/PD-L1 pathway in myeloid derived malignancies remains poorly understood, but may offer an innovative approach at targeting the MPN hematopoietic stem cell and disrupting supporting signals from the stromal niche. Ongoing pre-clinical studies assessing the expression and function of PD-1 pathway in MPN primary cells is ongoing as a collaboration between the PI of this trial and Merck. These laboratory studies will provide insight into the role of PD-1 in escape of immune suppression of the malignant clone as well as progression and evolution of the malignant clone and the role the supporting bone marrow and splenic stroma may provide. However, it remains unclear at present if expression of PD-1 or PD-L1 by MPN cells or supporting stromal cells will predict response to pembrolizumab. Correlative studies within this trial will measure levels of expression of PD-1 and PD-L1 at baseline, after treatment with pembrolizumab at time of response assessment or at time of treatment discontinuation for any reason.

Currently, ruxolitinib is the only FDA-approved therapy for the treatment of MF and patients that have either primary or secondary resistance or intolerance to this agent have been shown to have a particularly poor outcome. No established standard of care exists for these patients. Additionally, patients with MPN-AP/BP have a dismal prognosis and there is no standard of care therapy for these patients. Outside of hematopoietic stem cell transplantation (HSCT), which is only a viable therapeutic option for a fraction of these patients, no other therapies have demonstrated clear disease course modification. Therefore, effective treatment options for these patients with advanced MPN are urgently needed. This is the subset of MPN patients that will be included in this phase II trial of pembrolizumab with a primary objective of disease response assessment after 6 cycles.

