4.2.2 Rationale for Dose Selection/Regimen/Modification

An open-label Phase I trial (Protocol 001) was conducted to evaluate the safety and clinical activity of single agent pembrolizumab. The dose escalation portion of this trial evaluated three dose levels, 1 mg/kg, 3 mg/kg, and 10 mg/kg, administered every 2 weeks (Q2W) in subjects with advanced solid tumors. All three dose levels were well tolerated and no dose-limiting toxicities were observed. This first in human study of pembrolizumab showed evidence of target engagement and objective evidence of tumor size reduction at all dose levels (1 mg/kg, 3 mg/kg and 10 mg/kg Q2W). No MTD has been identified to date. 10.0 mg/kg Q2W, the highest dose tested in PN001, determined the dose and schedule utilized in Cohorts A, B, C and D of this protocol to test for initial tumor activity. Recent data from other clinical studies within the pembrolizumab program has shown that a lower dose of pembrolizumab and a less frequent schedule may be sufficient for target engagement and clinical activity.

PK data analysis of pembrolizumab administered Q2W and Q3W showed slow systemic clearance, limited volume of distribution, and a long half-life (refer to IB). Pharmacodynamic data (IL-2 release assay) suggested that peripheral target engagement is durable (>21 days). This early PK and pharmacodynamic data provides scientific rationale for testing a Q2W and Q3W dosing schedule.

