4.2.4.4 Biomarker Research

Immunotherapy as a target in MPN has not been extensively studied. As such, an important component of this study will be to gain better understanding of markers that predict outcome and response to PD-1 therapy.

1. Biomarker: Assess expression of PD-1/PD-L1 on peripheral blood PB-MNCs, T-cells and CD34+cells by flow cytometry:

Up-regulated PD-1 expression on peripheral blood MNCs and PD-L1 on MPN CD34+cells provides an inappropriate immune tolerance signal allowing for disease progression. Pre-clinical data suggests that PD-1 and PD-L1 are upregulated in patients with MDS and AML, especially in those who have received prior treatment. As part of this clinical trial we will test PD-1 and PD-L1 expression in circulating T-cells and tumor cells, respectively, to evaluate if expression of these molecules correlates with disease status and response to treatment.

Expected result: PD-1 expression is up-regulated on PB MNC and T-cells and PD-L1 is up-regulated on MPN HSC from patients enrolled on this trial at baseline.

Assay: Expression of PD-1 and PD-L1 will be measured by flow cytometry on cells from the peripheral blood of treated patients at baseline and at the start of cycle 3 (9 weeks).

2. Biomarker: Assess expression of PD-1/PD-L1 on bone marrow CD34+cells and supporting stromal cells by immunohistochemical staining

Up-regulated PD-1 expression on peripheral blood MNCs and PD-L1 on MPN CD34+cells provides an inappropriate immune tolerance signal allowing for disease progression. Pre-clinical data suggests that PD-1 and PD-L1 are upregulated in patients with MDS and AML, especially in those who have received prior treatment. As part of this clinical trial we will test PD-1 and PD-L1 expression in circulating T-cells and tumor cells, respectively, to evaluate if expression of these molecules correlates with disease status and response to treatment. Expression of CD45 surface marker will be evaluated in parallel with PD-1 and/or PD-L1 expression to differentiate between stromal (CD45 positive) and hematopoietic cells (CD45 positive) within the bone marrow.

Expected result: PD-1 expression is up-regulated on PB MNC and T-cells and PD-L1 is up-regulated on MPN HSC from patients enrolled on this trial at baseline.

Assay: Expression of PD-1 and PD-L1 will be measured by immunohistochemistry on bone marrow.

3. Biomarker: Assess PD-1/PD-L1 DNA methylation status by bisulfite-sequencing assay

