Changes in gene methylation status correlate with protein expression. Little is known about the significance of methylation status and PD-1/PD-L1 expression in MPN. Differences in methylation status in MDS have been used to characterize different MDS risk groups as a result of epigenetic dysregulation.

Assay: We will measure PD-1/PD-L1 gene methylation status by bisulfite-sequencing assay.

Expected result: Differential methylation will correlate with expression levels of PD-1/PD-L1, which in turn will correlate with disease status and response to PD-1 antibody therapy. These results will be instrumental in determining treatment strategies after hypomethylating agent failure in MPN-AP/BP based on their PD-1 expression status and additionally may suggest a role for hypomethylating agent priming prior to PD-1 inhibition in MF-CP patients.

4. Biomarker: Assess status and change in PD-1/PD-L1 expression with response to therapy.

PD-1/PD-L1 expression has been investigated in a variety of malignancies as biomarkers of response to therapy, little is known about the significance of PD-1 and PD-L1 expression in MPN and if these markers are surrogates for disease response.

Expected result: Changes in PD-1 and PD-L1 expression, as measured in exploratory aims 1-3, will correlate with disease response assessed by conventional response criteria (IWG-ELN).

5. Biomarker: Assess changes in driver mutation burden (*JAK2V617F*, *MPLW515L/K*, *CALR*) in granulocytes from treated patients at diagnosis, after 6 cycles and at 1 year of pembrolizumab therapy and correlate with response to therapy.

Changes in mutational status allele burden may correlate with disease response. In addition, it is unknown if patients with different mutations will respond preferentially to PD-1 therapy. We will correlate mutational status as well as change in allele burden with disease status and response to therapy and with expression of PD-1 and PD-L1.

Expected Result: Driver mutation burden will decrease in response to pembrolizumab therapy.

Assay: In order to assess changes in driver mutation burden we will use the rapid heme panel for next generation sequencing at Brigham and Women's hospital.

6. Biomarker: Evaluate changes in Immune response gene expression profile as well as tumor microenvironment in bone marrow biopsy specimens using nanostring technology after 6 cycles of treatment with pembrolizumab

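### Response is tested only against PD-1/PD-L1 positivity at cycle 3, a category the plan does not define; neither baseline expression nor change in expression is related to response

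*Combined protocol and SAP*

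**What the plan says.** Section 4.2.1 states the open question: "it remains unclear at present if expression of PD-1 or PD-L1 by MPN cells or supporting stromal cells will predict response to pembrolizumab". Section 4.2.4.4 calls the search for markers of outcome and response an important part of the study. Its item 4 expects this: "Changes in PD-1 and PD-L1 expression, as measured in exploratory aims 1-3, will correlate with disease response". The title of Section 8.2.4.4 likewise promises both status and change in relation to response.

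The analysis given in 8.2.4.4 is a single comparison. Response after the sixth cycle is compared between positive and negative patients, "with positivity based on 3rd cycle expression levels, using a Fisher's exact test of association".

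The only rule for calling a patient positive is in 8.2.4.2: staining intensity of at least 2 in more than 5% of tumor cells, read on marrow by immunohistochemistry. Section 8.2.4.1 summarizes blood flow cytometry by fluorescence intensity and percentage of cells and sets no threshold. The flow chart and Table 8 schedule blood at baseline and cycle 3. Table 8 marks marrow as not collected at cycle 3.

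On timing, Section 2.1 says: "A treatment cycle is 3 weeks and the core study period is 6 cycles". Section 4.2.4.4, item 1, places the blood measurement "at baseline and at the start of cycle 3 (9 weeks".

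**The concern.** A marker that is meant to predict response, or to help select patients, has to be known before treatment. The cycle 3 value is first available after two doses, and the plan never sets the pre-treatment value against response although it is collected. The stated question would therefore go unanswered with the data in hand.

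Three further problems follow from the cycle 3 choice.

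- The classification cannot be carried out as written, so whoever runs the analysis would have to choose a compartment and a cut-off after seeing the data.
- Biomarker analyses use the Full Analysis population (8.1.1.2), which requires one cycle and one post-baseline efficacy assessment. A patient who leaves between cycle 1 and cycle 3 day 1 can be in that population as a non-responder with no cycle 3 value, and no handling is stated. Missing values would then be linked to outcome.
- The promised analysis of change is absent. Sections 8.2.4.1 and 8.2.4.2 test change from baseline without reference to response. Section 8.2.4.5 ends with mean changes in PD-1 and PD-L1 over time, again not by response.

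**Working it through.** **1. The plan's own figure.** The documents give no size or power for the biomarker test. Its sample size comes from the Simon design in 4.2.3: stop if 0 of 9 respond, declare activity if at least 3 of 24 respond, with rates 5% and 25%.

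P(declare active) = sum over x = 1 to 9 of C(9,x) p^x (1−p)^(9−x) × P(Bin(15,p) ≥ 3−x).

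- p = 0.25: 0.903 (plan: 0.90).
- p = 0.05: 0.093 (plan: 0.10).

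The design reproduces, so up to 24 primary-cohort patients are available. The exploratory cohort is summarized separately (8.1).

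**2. Timing.** Cycles last 21 days.

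- Start of cycle 3 = 1 + 2 × 21 = day 43, that is 6 weeks, after two doses.
- Nine weeks = 63 days, that is day 64 = 1 + 3 × 21, the start of cycle 4, after three doses.
- The flow chart and Table 8 both tie the sample to cycle 3, so the 9-week label is the odd one out.
- Table 5 requires benefit to last at least 12 weeks, and assessment is at week 18 (6 × 3). If the 12 weeks must be complete by then, benefit starts no later than 18 − 12 = week 6, the nominal day of the cycle 3 sample. That sample then need not precede the response. The documents do not say whether later confirmation counts, so this is conditional.

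**3. Can cycle 3 positivity be assigned?**

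| Material | Cut-off in SAP | Baseline | Start of cycle 3 | End of cycle 6 |
|---|---|---|---|---|
| Marrow immunohistochemistry | Yes (8.2.4.2) | Yes | No | Yes |
| Blood flow cytometry | None | Yes | Yes | Yes |

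At cycle 3, the material with a cut-off is not collected and the material collected has no cut-off. At baseline, marrow has both.

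**4. What a Fisher test can show with 24 patients.** With a 12/12 split and all r responders in one group, the smallest two-sided p is 2 × C(12,r) / C(24,r).

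- r = 3: 2 × 220 / 2,024 = 0.217
- r = 4: 2 × 495 / 10,626 = 0.093
- r = 5: 2 × 792 / 42,504 = 0.037
- r = 6: 2 × 924 / 134,596 = 0.014

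Three is the smallest number that declares activity, and six is 25% of 24. An uneven split can do better, but only in the extreme case: with 8 positives and all 3 responders among them, p = C(8,3) / C(24,3) = 56 / 2,024 = 0.028.

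Exact power, assuming a 12/12 split, a two-sided 0.05 level (none is stated) and group response rates averaging 25%:

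- 40% v 10%: 0.23
- 45% v 5%: 0.48
- 50% v 0%: 0.81

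Moving to baseline status keeps the sample size at up to 24. It changes which question is answered, not how many patients answer it.

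**The case against.** The strongest defense is that this is one exploratory test in about 24 patients, that no go/no-go rule uses it, and that baseline samples are already planned, so a baseline analysis can be added at any time. Patients who do not complete one cycle are replaced (5.9), which limits the loss before cycle 3. Section 7.1.3.1 describes these measurements as pharmacodynamic, and a week 6 value still comes before the week 18 assessment. All of this stands. It lowers the importance of the point but does not supply a definition of cycle 3 positivity, a baseline test or an analysis of change.

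A reader might go further and infer that PD-1 at cycle 3 will read close to absent in every patient because the drug covers the receptor, so that the test is empty. The documents do not support that. Section 4.2.2 says: "Pharmacodynamic data (IL-2 release assay) suggested that peripheral target engagement is durable (>21 days". That is a functional assay, worded as a suggestion, with no occupancy figure. Whether bound drug hides PD-1 depends on the detection antibody, which is not named. Any percentage loss of signal would only restate an assumed occupancy.

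Nor does the argument reach PD-L1. Pembrolizumab is "designed to directly block the interaction between PD-1 and its ligands, PD-L1 and PD-L2": it binds PD-1, not PD-L1. What remains is a conditional caution about PD-1 on blood cells. Doses are 21 days apart and procedures precede dosing (5.2.2), so on-treatment blood is drawn about 21 days after a dose, when engagement may persist.

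It would also be too strong to say that the cycle 3 test can show nothing. Once positivity is defined, it could show an early on-treatment association.

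**Conclusion.** The point holds in this form. The only test of expression against response uses an on-treatment category that the SAP does not define, while the trial's own questions about baseline expression and change have no test. This rests on setting the sections side by side and needs no assumption about the assay. The 9-week label is a separate, minor contradiction of three weeks.

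The consequence is limited to an exploratory endpoint; the primary result and both stopping decisions are unaffected. A corrected test will still be weak: with an even split it cannot reach 0.05 with 3 or 4 responders, and its power is 0.23 to 0.81 under the assumed differences above. Estimates with intervals are therefore the more useful output. The week 6 onset argument depends on the 12-week duration being complete at week 18, and the PD-1 caution depends on the unnamed detection antibody.

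**What to change.** 1. In 8.2.4.4, classify patients by baseline (screening) marrow positivity with the cut-off in 8.2.4.2 and use that status for the Fisher test. Report response rates in each group with exact confidence intervals, and the number of patients without a baseline status.
2. Add a descriptive comparison, between responders and non-responders, of the change in expression from baseline to end of cycle 6. State that it is concurrent with response and not predictive.
3. Keep cycle 3 blood values as descriptive on-treatment data. If a blood classification is wanted, fix its cut-off before analysis.
4. For PD-1 on blood cells only, state that a fall on treatment will not be read as a change in expression unless the detection antibody is confirmed not to compete with pembrolizumab.
5. Reconcile the 9-week label in 4.2.4.4 with the 3-week cycle, which puts the start of cycle 3 at week 6.

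Cost: SAP wording and one check on the flow reagent, with no new visits or scheduled samples. The cycle 3 association becomes descriptive. The flow chart also allows an outside marrow from up to three months before screening, with blood taken for correlative work instead. For those patients the biopsy block would have to be requested, or baseline status reported as missing.

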4.2.4 Rationale for Endpoints

4.2.4.1 Efficacy Endpoint

Primary endpoint:

1. The proportion of treated MF-CP patients (primary cohort) that achieve at least a clinical improvement (CI, PR, CR) by combined European Leukemia Net – International Working Group (ELN-IWG) criteria (Table 5) after 6 cycles of pembrolizumab therapy.

Secondary endpoint:

1. The proportion of treated MPN-AP/BP patients (exploratory cohort) that achieve at least a complete morphologic remission of the leukemic blasts (CR, Cri) by Acute Myeloid Leukemia Response Criteria (Table 6A) within 6 cycles of pembrolizumab therapy.
2. The proportion of treated MPN-AP/BP patients (exploratory cohort) that achieve at least an acute leukemia response-partial (ALR-P, ALR-C, CCR, CMR) using published consensus criteria by Mascarenhas et al. (Table 6B) within 6 cycles of pembrolizumab therapy.

4.2.4.2 Exploratory Endpoints:

1. Assess expression of PD-1/PD-L1 on peripheral blood PB-MNCs, T-cells and CD34+ cells by flow cytometry
2. Assess expression of PD-1/PD-L1 on bone marrow CD34+cells and supporting stromal cells by immunohistochemical staining
3. Assess PD-1/PD-L1 DNA methylation status by bisulfite-sequencing assay
4. Assess status and change in PD-1/PD-L1 expression with response to therapy.
5. Assess changes in driver mutation burden (*JAK2V617F*, *MPLW515L/K*, *CALR*) in granulocytes from treated patients at diagnosis, after 6 cycles and at 1 year of pembrolizumab therapy using the rapid heme panel for next generation sequencing at Brigham and Women's hospital and correlate with response to therapy.
6. Evaluate changes in immune response gene expression profile as well as tumor microenvironment in bone marrow biopsy specimens using nanostring technology after 6 cycles of treatment with pembrolizumab.

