5.8 Subject Withdrawal/Discontinuation Criteria

Subjects may withdraw consent at any time for any reason or be dropped from the trial at the discretion of the investigator should any untoward effect occur. In addition, a subject may be withdrawn by the investigator or the Sponsor if enrollment into the trial is inappropriate, the trial plan is violated, or for administrative and/or other safety reasons. Specific details regarding discontinuation or withdrawal are provided in Section 7.1.4 – Other Procedures.

A subject must be discontinued from the trial for any of the following reasons:

- The subject or legal representative (such as a parent or legal guardian) withdraws consent.
- Unacceptable adverse experiences as described in Section 5.2.1.2
- Subject did not achieve at least a CI response per Table 5 for the MF-CP cohort or at least PR for the MPN-AP/BP cohort per Table 6A at response assessment.

- Intercurrent illness that prevents further administration of treatment
- Investigator's decision to withdraw the subject
- The subject has a confirmed positive serum pregnancy test
- Noncompliance with trial treatment or procedure requirements
- The subject is lost to follow-up
- Administrative reasons

The End of Treatment and Follow-up visit procedures are listed in Section 6 (Protocol Flow Chart) and Section 7.1.5 (Visit Requirements). After the end of treatment, each subject will be followed for 30 days for adverse event monitoring (serious adverse events will be collected for 90 days after the end of treatment as described in Section 7.2.3.1).

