7.1.2.5 Assessment of Disease Response

Clinical response for patients with MF-CP in the primary cohort will be evaluated using the Revised IWG-MRT and ELN response criteria for Myelofibrosis¹² as follows (patients must achieve at least CI to continue in the extension phase):

TABLE 5. International Working Group for Myelofibrosis Research and Treatment and European leukemiaNet (IWG-ELN) response criteria for myelofibrosis

Response categories	Required criteria (for all response categories, benefit must last for ≥12 weeks in order to qualify as a response)
Complete Remission (CR)	Bone marrow: * Age-adjusted normocellularity; <5% blasts; ≤Grade 1 myelofibrosis**, AND Peripheral blood: Hemoglobin ≥100 g/L and <UNL; Neutrophil count ≥1 x 10 ⁹ /L and <UNL; Platelet count ≥100 x 10 ⁹ /L and <UNL; <2% immature myeloid cells***, AND Clinical: Resolution of disease symptoms; Spleen and liver not palpable; No evidence of EMH
Partial Remission (PR)	Peripheral blood: Hemoglobin ≥100 g/L and <UNL; Neutrophil count ≥1 x 10 ⁹ /L and <UNL; Platelet count ≥100 x 10 ⁹ /L and <UNL; <2% immature myeloid cells***, AND Clinical: Resolution of disease symptoms; Spleen and liver not palpable; No evidence of EMH OR Bone marrow: * Age-adjusted normocellularity; <5% blasts; ≤Grade 1 myelofibrosis**, AND Peripheral blood: Hemoglobin ≥85 but <100 g/L and <UNL; Neutrophil count ≥1 x 10 ⁹ /L and <UNL; Platelet count ≥50 but <100 x 10 ⁹ /L and <UNL; <2% immature myeloid cells***, AND Clinical: Resolution of disease symptoms; Spleen and liver not palpable; No evidence of EMH
Clinical improvement (CI)	The achievement of anemia, spleen or symptoms response without progressive disease or increase in severity of anemia, thrombocytopenia or neutropenia‡
Anemia response	Transfusion-independent patients: a ≥20 g/L increase in hemoglobin level† Transfusion-dependent patients: becoming transfusion-independent††
Spleen response§	A baseline splenomegaly that is palpable at 5-10 cm, below the LCM, becomes not palpable§§, OR A baseline splenomegaly that is palpable at >10 cm, below the LCM, decreases by ≥50%§§ A baseline splenomegaly that is palpable at <5 cm, below the LCM, is not eligible for spleen response

	A spleen response requires confirmation by MRI or CT showing $\geq 35\%$ spleen volume reduction

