7.1.5.2 Treatment Period

The treatment period will consist of 3 week cycles in which the study drug will be given on day 1 of each cycle and the following tests and procedures will be obtained: prior con med review, adverse event review, physical exam with attention to spleen length in craniocaudal direction measured by a ruler at the mid clavicular line from the costal margin, vitals, ECOG, CBC and comprehensive serum chemistry, and thyroid function tests (on C3D1).

The core study period is a total of 6 cycles (study visits and drug administration will take place on day 1 of each cycle and the window is +/- days). Response assessment visit will take place on cycle 7 day 1 which will include the addition of a bone marrow biopsy and aspiration and biomarker evaluation from the aspirate and peripheral blood. The PI will decide if the subject will continue receiving therapy in the extension phase (Cycle 7+) of the trial as long the following is true: at least a clinical improvement by IWG-ELN criteria (Table 5) for chronic phase patients and at least a partial response by Table 6A and 6B (secondary objective) for accelerated and blast phase patients; the absence of unacceptable toxicity; both patient and treating physician are in favor of continued treatment on protocol. Patients can continue receiving study drug in the extension phase as long as they do not meet criteria for discontinuation of treatment defined in Section 5.8 and to a maximum duration of 2 years

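### Among chronic-phase patients only responders continue to 1 year, so the 1-year change in driver mutation burden cannot be correlated with 6-cycle response, and Section 8.2.4.5 names no comparison by response at any time point

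*Combined protocol and SAP*

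**What the plan says.** Section 8.2.4.5 opens with the aim "To assess the correlation between changes in driver mutation burden from diagnosis to 1 year of pembrolizumab therapy and response to therapy". The methods that follow are:

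- median allele burden at baseline, after 6 cycles and at 1 year;
- a signed-rank test against baseline at each follow-up;
- a mixed model of log allele burden in mutation-positive patients, with a random patient effect and time as its only fixed effect.

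Response does not appear in any of them. The closing sentence speaks of changes in PD-1 and PD-L1, not of response.

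Section 4.2.4.1 defines response in MF-CP as CI, PR or CR after 6 cycles. Section 5.8 lists among the mandatory reasons for discontinuation: "Subject did not achieve at least a CI response per Table 5 for the MF-CP cohort". Section 7.1.2.5 repeats the gate ("patients must achieve at least CI to continue in the extension phase"), and Sections 2.1 and 7.1.5.2 agree with it.

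Once treatment stops, follow-up is short: "After the end of treatment, each subject will be followed for 30 days for adverse event monitoring", with serious events collected to 90 days. Table 8 adds a blood draw at discontinuation. That is not a 1-year sample.

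Section 8.2.4.6 also uses the 1-year time point, describing gene-expression signatures "before therapy as well as at 6 cycles and 1 year post therapy".

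**The concern.** The aim relates two quantities, the change in burden to 1 year and response to therapy. The protocol's continuation rule fixes one of them for every MF-CP patient in whom the other can be observed. Better sampling or a larger trial would not change that.

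A second problem lies in the summaries. Nothing requires the three medians to come from the same patients. If burden at baseline differs between patients who later respond and those who do not, the median can move between baseline and 1 year with no change in any individual. The direction of that shift cannot be known in advance.

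At stake is whether the trial can answer its own exploratory question about clonal burden and response, and whether a reader would take a lower 1-year median as an effect seen across the cohort.

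**Working it through.** **Inputs.** From Section 4.2.3: 24 MF-CP patients (9 + 15), response rates of 5% (inactive) and 25% (active), stated error 0.10 and power 0.90. From Sections 2.1, 5.8, 7.1.2.5 and 7.1.5.2: at least CI is needed to go past cycle 6. The plan gives no figure for the mutation analysis itself, no mutation frequencies, and no expected proportion still on treatment at 1 year.

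**The plan's own figure.** For the two-stage rule (stop at 0 of 9, otherwise require at least 3 of 24), the probability of declaring activity is the sum over x = 1 to 9 of Bin(9, x, p) × P(Bin(15, p) ≥ 3 − x). At p = 0.25 this is 0.903, which reproduces the stated 0.90. At p = 0.05 it is 0.093, within the stated 0.10. The 24 patients and the 25% rate are therefore a sound basis for what follows.

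**Can the correlation be computed?** In MF-CP patients with a 1-year on-therapy value, 6-cycle response is always yes. Its variance is 0, so a correlation or a two-group comparison with the 1-year change is undefined. At the post-cycle-6 assessment both groups exist.

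| Response rate | Post-cycle-6: responders / non-responders | 1 year: responders / non-responders |
|---|---|---|
| 25% | 24 × 0.25 = 6 / 18 | about 6 / 0 |
| 5% | 24 × 0.05 = 1.2 / 22.8 | about 1.2 / 0 |

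These are expectations. They take all 24 patients as enrolled and, at 1 year, every responder as still on treatment.

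**How many reach 1 year?** With X ~ Bin(24, p), P(X ≥ 6) is 0.58 at 25% and 0.001 at 5%. If 75% or 50% of responders are still treated at 1 year (assumed), the expected number at a 25% response rate is 4.5 or 3.0, and P(≥ 6) is 0.29 or 0.07.

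**Per mutation.** Assume a mutation is carried by a fraction f of patients, independently of response, and that every responder stays on treatment. Then X ~ Bin(24, 0.25f):

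| f (assumed) | Expected 1-year pairs | P(at least 6 pairs) |
|---|---|---|
| 0.4 | 2.4 | 0.028 |
| 0.6 | 3.6 | 0.139 |
| 0.8 | 4.8 | 0.344 |

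Six matters because the smallest two-sided exact signed-rank p-value is 2/2^n: 0.0625 at n = 5 and 0.031 at n = 6.

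**What each listed method can show at 1 year.**

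- Medians: baseline covers all mutation-positive patients and 1 year covers continuing responders, so the two differ in composition.
- Signed-rank test: it works within patients, so a change in composition cannot create its result. It describes continuing patients.
- Mixed model: it can be fitted, but its 1-year mean stands for the whole cohort only under a missing-at-random assumption that the plan does not state.

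None of the three tests association with response.

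**The case against.** The strongest reply is that no specified test fails. The medians, signed-rank tests and mixed model can all be computed at 1 year. The section also covers the 6-cycle time point, where non-responders can contribute. This stands. A reader might infer that the whole mutation analysis is unworkable, or that any fall by 1 year merely shows who was kept on treatment. The documents support neither reading: the paired test is sound for continuing patients, and only the unpaired medians mix different groups.

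It can also be said that response need not be binary or fixed at 6 cycles. Table 5 has grades and a relapse category, and patients in the accelerated/blast-phase cohort may continue on a Table 6A partial response without meeting the CR/CRi endpoint. This softens the point. However, Section 8.2.4.5 names no such definition, about six MF-CP patients could not support one, and Section 8.1 summarizes the other cohort separately.

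A reader might carry the full criticism over to Section 8.2.4.6. That section specifies no 1-year test and no 1-year comparison by response, so only a caution about who is sampled applies.

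Finally, the post-cycle-6 comparison has its own selection. The flow-chart footnote and Section 7.1.5.3.1 secure the cycle 7 day 1 procedures for patients known to be missing the response, but patients who stop earlier, for example for toxicity, may have no such sample. That is correct and has to be reported.

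**Conclusion.** The point holds within limits. For MF-CP, the correlation of the 1-year change with 6-cycle response is undefined by design, and Section 8.2.4.5 supplies no response comparison at any time point to take its place. The baseline and 1-year medians describe different patients. The 1-year signed-rank test is valid but speaks only for patients who continued as responders.

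About 6 of 24 MF-CP patients are expected to be eligible to reach 1 year at a 25% response rate. A reader might take six as a ceiling, but it is an expectation, with probability 0.58 of six or more. The per-mutation counts rest on assumed carriage of 40% to 80%, independence of mutation and response, and full retention of responders. The undefined correlation depends on none of these. It rests only on reading response as CI or better after 6 cycles, which is the plan's own endpoint.

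The matter is minor. It concerns one exploratory biomarker, and no primary, secondary, safety or stopping decision depends on it.

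**What to change.** In Section 8.2.4.5:

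1. Define the response analysis as the change in allele burden from baseline to the post-cycle-6 sample, compared between responders and non-responders within each cohort. Name the response definition used for each cohort.
2. Report how many patients lack that sample because they stopped before cycle 7 day 1.
3. Report the baseline, post-cycle-6 and 1-year medians in the one subset of patients with 1-year data, alongside any full-cohort baseline summary.
4. Label all 1-year results as descriptive of patients who continued as responders. The signed-rank test may stay under that label; removing it would be a matter of preference.

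In Section 8.2.4.6, add the same label to the 1-year gene-expression summary.

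The cost is SAP wording only. No visit, sample or treatment rule changes. The comparison by response will still be small, about 6 against 18 at a 25% response rate before splitting by mutation and before early stoppers are removed, so it should be presented as exploratory.
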